2.2.3 Modified Intent-to-Treat (mITT) Population

The modified intent-to-treat Population (mITT) will consist of all subjects who have received ublituximab and have one baseline and post-baseline MRI.

2.2.4 Other Analysis Population

The PK Population will be a subset of the Safety Population containing subjects who participate in the population PK subset and have at least one baseline and one post-baseline PK sample taken.

2.3 Disposition of Subjects

Subject disposition will be tabulated as follows:

- Screened subjects defined as subjects who signed the informed consent;
- Screened but not randomized subjects and reasons for not randomized (screen failure etc.);
- Randomized subjects and corresponding treatment;
- Subjects who completed the 48-week study treatment period
- Subjects who discontinued study treatment and reasons for discontinuation but continue to allow assessments in the study after stopping study medication;

For all categories of subjects (except for the screened and non-randomized categories) percentages will be calculated using the number of randomized subjects per cohort as the denominator.

Additionally, the analysis populations for safety, ITT and mITT will be summarized in a table by subject counts on the randomized population.

2.4 Statistical Methods

Unless otherwise stated, all analyses will be performed using SAS Version 9.2 or higher. All hypothesis tests will be descriptive and conducted at a two-sided significance level of 0.05; no

multiplicity adjustment will be done. P-values will be presented with 3 decimals and p-values that are less than 0.001 will be presented as <0.001.

2.4.1 Demographics and Baseline Characteristics

Continuous data will be summarized using number with available data: mean, standard deviation (SD), median, minimum, and maximum, and 1st and 3rd quartile for each treatment group. Categorical or ordinal data will be summarized using the number and percentage of subjects within each treatment group. Summaries will be presented for the ITT population.

Demographics and Baseline Characteristics

Demographic and baseline characteristics as described in Section 2.1.1 will be summarized by treatment cohort and overall using descriptive statistics.

Medical and surgical history

Medical history and concurrent medical conditions (ongoing at screening) will be summarized by primary system organ class (SOC) and preferred term for each treatment cohort. The table will be sorted alphabetically by SOC and by decreasing frequency in the total column.

Concomitant/follow-up medications

The concomitant and follow-up medications will be presented on the safety population.

Medications will be summarized by treatment cohort, according to the international classification of medicines (WHO-DD dictionary), using the terms corresponding to the ATC class level 4 and Preferred Name. All ATC codes corresponding to a medication will be summarized. Subjects will be counted once in each ATC categories (anatomic or therapeutic) linked to the medication.

The tables for concomitant and follow-up medications will be sorted by decreasing frequency of anatomic category followed by all other therapeutic classes based on the incidence in the total column. In case of equal frequency regarding anatomic categories or therapeutic categories, alphabetical order will be used.

Previous MS treatment

Variables related to previous MS treatment will be summarized per treatment cohort.

No statistical tests will be performed on demographic and baseline characteristic data.

2.4.2 Primary Efficacy Variable

The primary efficacy variable will be responder rate of B-cell depletion at week 4, which is the proportion of subjects who have reduced B-cell depletion at week 4 (2 weeks after W3D15 administration of ublituximab) in the ITT population. The percentages of the responders and its 95% confidence intervals will be presented by cohort and total, if appropriate, using exact method due to small sample size. The B-cell count in % and its change from baseline will be summarized by visit. Logistic analysis may be used to perform trend tests to assess dose response.

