Products	Ublituximab is a recombinant chimeric monoclonal antibody against the CD20 antigen, available as a 10 mg/mL or 25mg/mL concentrate for solution for infusion, supplied by TG Therapeutics, Inc.

Phase	Phase IIa
Study Sponsor	TG Therapeutics, Inc. (New York, NY, USA)
Study Chair	RMS Group Study Chair ██████████, MD, PhD ██████████ ██ ██ ██
Study Objectives	
Primary Objectives
 
 
To determine the level of B cell depletion by ublituximab in subjects with RMS
 
To determine the optimal dose and infusion time for ublituximab in subjects with RMS
 
 
Secondary Objective
 
 
To examine the effect of ublituximab on the development of new Gadolinium-(Gd) enhancing lesions and new or enlarging T2 lesions at 24 and 48 weeks
 
To evaluate the % of relapses in ublituximab-treated RMS subjects
 
To determine immunogenicity
 
To evaluate the safety of ublituximab, as determined by adverse events (AEs) and serious adverse events (SAEs), including MS worsening
 

Efficacy Endpoints	
Efficacy Endpoints
 
 
Responders Rate defined as percent of subjects with ≥95% reduction of B cells (CD19+ cells) within 2 weeks after the second infusion (day 15)
 
 
Secondary efficacy endpoints
 
 
Number of new Gd-enhancing lesions at 24 and 48 weeks
 
Number of new or enlarging T2 lesions at 24 and 48 weeks
 
Annualized relapse rate (ARR)
 
Relapse rate reduction (RRR)
 
Percent of relapse free subjects
 
Reduction in B cells (CD19+), memory (CD19+CD27+) and naïve (CD19+CD27-) B cells at baseline, day 1 (pre dose), 2, week 2, Day 15 (pre-dose), week 4 and every 4 weeks thereafter until the next infusion at weeks 24 (pre-dose and 2 days post dose) 25, 28, 36, 40, 44 and 48.
 
Additional immune profiling (CD4+, CD8+, IL10 and NK cells) at baseline, day 1 (pre dose), 2, week 3, 15 (pre-dose), week 4 and every 4 weeks thereafter until the next infusion at week 24 (pre-dose and 2 dose post-dose) 25, 28, 36, 40, 44 and 48.
 
PK (ADME) profile of ublituximab at day 1 and 15 and weeks 4, 24 and 25
 

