Safety Endpoints	All AEs will be reported and evaluated during the treatment period using National Cancer Institute (NCI) version 4.0 grading system; the number and severity of infusion-associated events, defined as AEs reported during or within 24 hours of an infusion; the number and severity of infectious AEs; any clinically significant changes in laboratory or vital sign measurements; the incidence of anti-drug antibodies (antibodies developed against ublituximab) to assess safety over the 52-week trial.
Study Design	This is a 52-week, phase IIa, placebo-controlled, multi-center study that is primarily designed to assess the optimal dosing, optimal infusion time as well as safety/tolerability of ublituximab (TG1101; UTX) in patients with RMS.

Subjects may be screened up to 4 weeks before first dosing date. Qualified subjects will receive ublituximab on Days 1, 15, and week 24. There will be at least four treatment cohorts in the study with 8 subjects (2 placebo and 6 ublituximab treatment; please see treatment schema) enrolled in each cohort. Subjects within each cohort will receive either placebo or study drug dosing on Days 1 and 15 and week 24 per dosing schema (please see table below). Additional dose ranging cohorts may be explored and expansion cohorts at selected doses are contemplated.

A Data and Safety Monitoring Board (DSMB) will be established to safe guard the wellbeing of the subjects and to advise the Sponsor whether it is appropriate to expand the enrollment to a dosing cohort or to initiate next dosing cohort. The DSMB may recommend to the Sponsor to terminate the enrollment to a treatment cohort for safety concerns or otherwise. For example, the DSMB may recommend early termination of enrollment to a dosing cohort that is higher than the optimal treatment cohort after the optimal dosing is determined or a cohort that is considered without meaningful clinical benefit.

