## 1.3 RATIONALE

### 1.3.1 CLINICAL STUDIES WITH RITUXIMAB AND OCRELIZUMAB

In vivo and in vitro studies have shown that B cells contribute to tissue damage in MS. B cells may enhance autoimmune processes through the presentation of autoantigens. Additionally, B cells can modulate the effector function of other autoimmune cells by producing soluble inflammatory mediators. In MS, B cells are believed to cross the blood brain barrier (BBB) and undergo stimulation, antigen-driven affinity maturation and clonal expansion within the CNS environment.[8] B cells are the source of differentiating plasma cells which secretes autoreactive antibodies, which may contribute to the demyelinating events in the CNS.

The CD20 molecule is expressed on pre-B cells and throughout the lifecycle of both naïve and memory B cells. It is not expressed on stem cells or pro-B cells at the earliest stages of B cell differentiation. Further, it is not expressed on plasmablasts or terminally differentiated plasma cells. Thus, CD20 is an ideal target for B cells targeted immunotherapy. Rituximab was the first anti-CD20 monoclonal antibody (mAb) to be tested in RRMS patients. The rituximab Phase I trial, a 72 week open-label study consisting of 26 enrolled RRMS patients, demonstrated that B-cell depletion was approximately 99.8% depleted by week 2 and sustained through week 48 when patients were treated with rituximab (500mg day 1; 500mg day 15).[9] Further, rituximab showed a 96% reduction in Gd-enhancing lesions at week 24 with 100% reduction by week 72. Clinically, the annualized relapse rate (ARR) at 48 and 72 weeks were 0.25 and 0.22, respectively, which equated to 81% and 83% reduction from baseline, respectively. The phase II (HERMES) study similarly demonstrated significant reduction in MRI and clinical activities, 91% reduction in the total number of Gd-enhancing lesions at weeks 12, 16, 20 and 24 compared to placebo and 42.3% reduction in relapse rate compare to placebo at 48 weeks.[10]

The second anti-CD20 mAb tested in RRMS patient was ocrelizumab. In its phase II study, similar to rituximab, there were significant reductions in both radiological and clinical activities.[11] In patients treated with ocrelizumab (600mg), there was an 89% reduction in total number of Gd-enhancing lesions for weeks 12, 16, 20 and 24 when compared to placebo. Clinically, ocrelizumab treated patients achieved an 80% reduction in relapse

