## 9.8 EFFICACY ANALYSES

---

The study is not designed (powered) to detect treatment differences. All efficacy variables will be summarized at all-time scheduled points where they are assessed. If appropriate, dose response or treatment differences may be analyzed. If p-values are presented, they will be nominal p-values without adjustment for multiple tests.

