- Concomitant medications (extension) are those taken at any time between last study treatment and end of extension.

Technical details related to calculating dates, imputation for missing dates, etc. are described in Section [2.5](#).

[2.1.2 Study Treatment Exposure](#)

Treatment exposure for ublituximab/placebo is summarized with following variables:

- The total number of infusions of placebo
- The total number of infusions of ublituximab received over the 3 expected infusions.
- The overall number of infusions of ublituximab, number and percentage (based on all infusions) of infusions completed with/without interruption and infusions not completed.
- The number and percentage of patients (based on all patients with at least one infusion) with and without any infusion complication (interruption or stop).
- The percentage of planned total infusion received.

[2.1.3 Efficacy Variables](#)

[2.1.3.1 Primary Efficacy Variable](#)

The primary efficacy variable will be responder rate at week 4 (2 weeks after W3D15, the second scheduled infusion of ublituximab), where responders are subjects who have reduced B-cell depletion by $\geq 95\%$.

[2.1.3.2 Secondary Efficacy Variables](#)

The secondary efficacy variables are as follows:

- Number of new Gd-enhancing lesions at 24 and 48 weeks
- Number of new or enlarging T2 lesions at 24 and 48 weeks
- Annualized relapse rate (ARR)
- Relapse rate reduction (RRR)
- Percent of relapse free subjects

- Reduction in B cells (CD19+), memory (CD19+CD27+) and naïve (CD19+CD27-) B cells at baseline, day 1 (pre dose) and 2; week 2; Day15 (pre-dose); week 4 and every 4 weeks thereafter until the next infusion at week 24 (pre-dose and 2 days post-dose) 25, 28, 36, 40, 44 and 48
- To examine sustained B cell reduction during the first and third infusions
- Additional immune profiling (CD4+, CD8+, IL10 and NK cells) at baseline, day 1 (pre dose) and 2; week 2, Day 15 (pre-dose); week 4 and every 4 weeks thereafter until the next infusion at week 24 (pre-dose and 2 days post dose) 25, 28, 36, 40, 44 and 48
- PK (ADME) profile of ublituximab at day 1 (pre-dose); week 2; day 15 (pre-dose); weeks 4, 24 (pre-dose) and 25

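### The only named dose-response test for B-cell depletion uses a 95% cut that may lie well inside the response; a continuous Week 4 analysis with a below-limit rule would use more of the data, though power for 600 vs 750 mg may stay low

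*SAP*

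**What the plan says.** The primary objectives are the level of B-cell depletion and the optimal dose and infusion time (protocol 2.1, SAP 1.2.1). SAP 2.1.3.1 states: "The primary efficacy variable will be responder rate at week 4", with a responder defined by a 95% cut; protocol 9.8.1 uses the same cut. For dose response, both documents say only: "Logistic analysis may be used to perform trend tests to assess dose response".

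The continuous data are not ignored. SAP 2.4.2 adds: "The B-cell count in % and its change from baseline will be summarized by visit". SAP 2.4.3 also summarises and plots the percentage reduction in B cells by visit. Protocol 9.8.2 lists that reduction as a secondary variable and allows dose response to be analysed as appropriate. None of these places names a method, a log scale or a rule for values below the assay limit.

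The one numerical depletion figure is for rituximab (protocol 1.3.1): "B-cell depletion was approximately 99.8% depleted by week 2". Detail on ublituximab's own effect in protocol 1.2.2.2 is partly redacted. The supplied text gives no SD, expected responder rate or detection limit. Protocol 9.8 says: "The study is not designed (powered) to detect treatment differences".

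**The concern.** A 95% cut treats 95.1% and 99.9% depletion as the same result. At 99.8% depletion the residual is 0.2% of baseline, 25 times below the 5% residual that defines a responder (5 / 0.2 = 25). If the regimens all work at about that depth, the responder table will show nearly everyone responding in every cohort, and a trend test on it has nothing to work with.

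The planned continuous summaries help only in part. Read as an absolute change, the change in B-cell percentage is close to minus the baseline value once the post-dose value is near zero. Read as a relative reduction, it shows depth but on a linear scale: 99.0% and 99.8% differ by 0.8 points although the residuals differ 5-fold (1% against 0.2%). The study is meant to inform the Phase 3 dose and infusion time, so depth is information worth keeping in the dose-response analysis.

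**Working it through.** The supplied text contains no sample-size or power figure, so there is none to reproduce.

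**Inputs from the documents**
- Each cohort is planned "with 8 subjects (2 placebo and 6 ublituximab treatment; please see treatment schema) enrolled in each cohort". The dosing tables list six cohorts, and placebo subjects cross to active treatment after Day 28.
- Before Week 4, cohorts 1-3 receive 150 + 450 = 600 mg and cohorts 4-6 receive 150 + 600 = 750 mg. That gives two cumulative doses, a ratio of 750/600 = 1.25, with 3 × 8 = 24 subjects each, or 3 × 6 = 18 without the cross-overs.
- SAP 2.4: tests are descriptive and "conducted at a two-sided significance level of 0.05".

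**Assumed, because not given**
- Residual CD19+ (Week 4 / baseline) is log-normal, with log10 SD (σ) 0.4-0.6.
- Median depletion at the lower dose is 97-99.8%.
- The true difference is 0.3-0.5 log10 (2.0- to 3.2-fold), or 1.25-fold if proportional to dose.
- The assay floor is 0.1%, 1% or 2% of baseline. There is no dropout.

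**Step 1: what the cut leaves.** With median residual m, the responder rate is Φ[(log10 0.05 − log10 m)/σ]. For m = 0.002 and σ = 0.5 this is Φ[(−1.301 + 2.699)/0.5] = Φ(2.80) = 99.7%. With no non-responders in one dose group, the other needs at least 3 of 24 for the likelihood-ratio test (p = 0.037) or 5 of 24 for Fisher's exact test (p = 0.0496). About 24 × 0.003 = 0.07 are expected. Even at a true rate of 99%, all 48 respond with probability 0.99^48 = 62%, and then no trend can be estimated.

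**Step 2: power, 24 vs 24.** The logistic likelihood-ratio test was enumerated exactly. The rank test (Mann-Whitney) was simulated with 4,000 runs per scenario. Ranges run over σ 0.4-0.6 and differences of 0.3-0.5 log10.

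| Median depletion, lower dose | Responder rate, lower dose | Logistic on cut | Rank, floor 0.1% | Rank, floor 1% | Rank, floor 2% |
|---|---|---|---|---|---|
| 97% | 64-71% | 25-76% | 37-99% | 36-98% | 33-96% |
| 98% | 75-84% | 22-61% | 37-98% | 33-97% | 29-89% |
| 99% | 88-96% | 6-35% | 37-99% | 31-90% | 24-64% |
| 99.8% | 99% or more | about 0% | 34-97% | 2-21% | 0-2% |

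With 18 vs 18 and a 0.1% floor, the logistic test has 0-66% and the rank test 27-94%. The smallest gain in any single scenario is then about 7 points.

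**Step 3: a dose-proportional difference.** At 1.25-fold with a 0.1% floor, the rank test has about 7-13% power over both group sizes. A t-test without a floor agrees: the noncentrality is (log10 1.25 / σ) × √(24/2) = (0.097/0.5) × 3.46 = 0.67, giving 10%. For 80% power with 24 vs 24 the difference must be 0.83 SD, that is 1.8-, 2.6- or 3.8-fold at SD 0.3, 0.5 or 0.7.

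**Step 4: ordered cohorts.** Scoring cohorts 1-6 with 8 each, SD 0.5, no floor and a 3-fold change from first to last, a trend test on the cut has 0% power at a median residual of 0.2% and 8% at 1%. Regression on the log residual has 60% and 58%.

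**Step 5: how low the assay must read.** Subjects may enter with B cells at 5% of lymphocytes. A floor of 0.1% of baseline then means resolving 5% × 0.001 = 0.005% of lymphocytes. If results were reported in steps of 0.1% of lymphocytes (an illustration), such a subject could not show a nonzero residual below 0.1/5 = 2% of baseline.

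**The case against.** The case against is substantial, and much of it stands.

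- **Depth is reported.** A reader might infer that the plan discards depth of depletion. It does not: SAP 2.4.3 summarises and plots B-cell reduction, and protocol 9.8.2 permits a dose-response analysis of it. SAP 2.4.7 also promises a separate plan for exposure-response analyses, without saying there which response. What is missing is a named continuous method.
- **Low power is disclosed.** The trend test is optional, p-values are nominal and the study is declared unpowered. Nothing says that a flat trend would be read as absence of dose response or would select the dose. This is lost information and not an error in a powered test.
- **The log scale does not guarantee power.** A reader might infer that a continuous test would recover it. The documents give no SD, effect size or assay limit, and only two close cumulative doses exist at Week 4. The gain shown needs a difference well above dose-proportional and a low enough assay floor.
- **The ceiling is inferred.** That nearly every subject will exceed 95% rests on an average for another antibody at another dose. At medians of 97-98% the responder rate is 64-84% and the logistic test has some power.
- **The form of the test matters.** At true rates of 90% vs 98% (24 per group), Fisher's test has 5.5% power and the likelihood-ratio test 28%. The comparison above therefore uses the latter, which is the reading kinder to the plan.

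What survives is that, at the one depletion level the documents cite, every version of the test on the cut has power near zero.

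**Conclusion.** The point holds as a recommendation to add a better-informed analysis. If depletion is near 99.8%, the named trend test has almost no ability to show a difference in depth, whichever logistic or exact version is used. At 99% it has 6-35% with 24 per dose. A rank test on the same measurements has 34-99% over all the scenarios with a 0.1% floor, against 0-76% for the cut.

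These figures rest on the assumed log10 SD of 0.4-0.6 and a 2- to 3.2-fold difference. They do not show that the Week 4 comparison of 600 with 750 mg would be well powered: at 1.25-fold, power is about 7-13%. At 99.8% depletion a floor of 1-2% of baseline leaves 0-21%. The continuous result is therefore best read as an estimate with a confidence interval.

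**What to change.** Keep the Week 4 responder rate with its exact confidence interval as the primary variable. In SAP 2.4.2 and protocol 9.8.1:

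1. Make the dose-response analysis one of log10(Week 4 CD19+ / baseline CD19+), using either a rank-based trend test (Jonckheere-Terpstra) or a Tobit model with values below the assay limit left-censored.
2. State the assay limit and the rule for zero or below-limit values: tied at the lowest rank, or censored at the limit divided by that subject's baseline.
3. Report the geometric mean residual as a percentage of baseline with a 95% confidence interval, by cohort and by cumulative dose, in addition to the planned summaries. Use the median if many values are below the limit.
4. Say that the result is an estimate with its interval, and that a non-significant trend is not evidence of equal depth.

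The cost is wording in the two documents and one extra table, with no new data. The downsides are that a censoring or tie rule has to be agreed, and that a log ratio is less familiar than a responder percentage, which is kept.

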2.4.3 Secondary Endpoints

MRI count variables:

- Number of new Gd-enhancing lesions at 24 and 48 weeks
- Number of new or enlarging T2 lesions at 24 and 48 weeks

The MRI count variables will be summarized by visit (baseline, 24 and 48 weeks) using descriptive statistics.

The Volume of Gd-enhancing lesions and T2 lesions at 24 and 48 weeks and the change from baseline will be summarized using descriptive statistics.

- Annualized relapse rate (ARR)
- Relapse rate reduction (RRR)
- Percent of relapse free subjects

ARR at week 48 is calculated as the ratio of the sum of all patients' confirmed relapse counts divided by the sum of all patients' treatment duration (in years). The confirmed relapses count includes the confirmed relapses starting (Start Date of Suspected Relapse Symptoms) on or after the day of first dose date of ublituximab and up to date of Week 48 visit or the early withdraw date, whichever occurs earlier. If the exact start date of relapse symptoms is unknown, the relapse will be assumed to have started during this period unless sufficient information is available to conclude that the symptoms started before or after (e.g. in case of missing start day, the symptoms start month is after the month of treatment end). ARR will be summarized by cohorts and total in ITT population.

Years under treatment will be derived as:

Treatment years = (date of Week 48 visit or early withdraw date – date of first dose of ublituximab + 1) / 365.25.

RRR will be calculated as the percentage reduction from baseline ARR to ARR at week 48. Baseline ARR will be the sum of (Total # of Relapses Within 1 Year Prior to Screening collected from CRF) divided by the number of subjects.

The percent and its 95% CI of relapse free subjects during the treatment period in ITT population will be presented.

- Reduction in B cells (CD19+), memory (CD19+CD27+) and naïve (CD19+CD27-) B cells at baseline, day 1 (pre dose) and 2; week 2; Day15 (pre-dose); week 4 and every 4 weeks thereafter until the next infusion at week 24 (pre-dose and 2 days post-dose) 25, 28, 36, 40, 44 and 48
- To examine sustained B cell reduction during the first and third infusions

The reduction in B cells (%) will be summarized and plotted by visit using descriptive statistics.

- Additional immune profiling (CD4+, CD8+, IL10 and NK cells) at baseline, day 1 (pre dose) and 2; week 2, Day 15 (pre-dose); week 4 and every 4 weeks thereafter until the next infusion at week 24 (pre-dose and 2 days post dose) 25, 28, 36, 40, 44 and 48

Descriptive statistics will be presented by visit.

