### 3.1 INCLUSION CRITERIA

---

1. 18-55 age
2. Diagnosis of RMS (McDonald criteria 2010; Appendix C)
3.  $\geq 2$  relapses in prior 2 years or 1 relapse in the year prior to screening and/or  $\geq 1$  Gd enhancing lesion
4. Active disease
5. EDSS 0-5.5 (inclusive)
6. B cell counts  $\geq 5\%$  of total lymphocytes
7. Neurologic stability  $\geq 30$  days prior to screening and baseline
8. Female subjects who are not of child-bearing potential, have documented surgical sterilization (see Appendix A), and female subjects of child-bearing potential who have a negative serum pregnancy test at baseline. Female subjects of child-bearing potential (see Appendix A), and all male partners must consent to use a medically acceptable method of contraception throughout the study period and for 30 days after the last dose of either study drug.
9. Willingness and ability to comply with trial and follow-up procedures, give written consent

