### 7.1.4 RELAPSE ASSESSMENT

Relapses are defined as the occurrence of new or worsening neurological symptoms attributable to MS, and immediately preceded by a stable or improving neurological state of at least 30 days. Symptoms that persists for more than 24 hrs in the absence of fever and be accompanied by objective neurological worsening consistent with an increase  $\geq 0.5$  on the EDSS (subjects with baseline EDSS of  $>1.0$ ) or an increase  $\geq 1.0$  on the EDSS (subjects with baseline EDSS=0).

Subjects will be assessed for relapse by the treating investigator at each study visit as outlined in the study evaluations table and, if necessary, at unscheduled visits. If a protocol defined relapse does occur, it will be documented in the eDC.

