2.1.1 Demographics and Baseline Characteristics

Demographic and other baseline characteristics

Demographic variables are gender (Male, Female), race (White, Black or African American, Asian, American Indian or Alaska Native, Native Hawaiian or Other Pacific Islander, Other, or Not Applicable due to country's legislation), age in years (quantitative and categorical variable: <38, and \geq 38 years) and Ethnicity (Hispanic or Latino, Not Hispanic or Latino, Not Reported, Unknown)

Medical and surgical history

Medical history data will be coded to “Preferred Term (PT)” and associated primary “System Organ Class (SOC)” using the Medical Dictionary for Regulatory Activities (MedDRA) version 23.0.

Disease characteristics at baseline

- Number of relapses experienced within past 1 year and 2 years (0, 1, 2, 3, and \geq 4), respectively
- Time since first diagnosis of MS (in years) to be derived as (Day of randomization – Day of first MS diagnosis) / 365.25
- Time since first symptoms of MS (in years) to be derived as (Day of randomization – day of first symptoms of MS) / 365.25
- Time since most recent relapse onset (in months) to be derived as (Day of randomization – day of most recent relapse onset) / (365.25 / 12)
- Baseline EDSS score
- Baseline EDSS (\leq 3.5, $>$ 3.5)
- Number of baseline Gadolinium (Gd)-enhancing lesions (0, \geq 1)
- Baseline T2 lesion count
- Baseline T2 lesion Volume
- Baseline brain volume

Multiple Sclerosis treatment history

- Received any MS therapy for at least 1 month (30 days) prior to enrollment (Yes, No)
- Prior Treatments for Current Diagnosis by Preferred Name
- Previous corticosteroid treatment for relapse
- Time since last corticosteroid treatment for relapse (months)

Vital signs and height

Vital signs are variables: weight in kg (quantitative variable and categorical variable: <50, \geq 50 - <100, \geq 100), height (m) and Body Mass Index (BMI) in weight[kg]/height[m²] (<30, \geq 30) calculated from weight and height.

Concomitant medications

All concomitant medications or concomitant medications (extension) are reported in the case report forms (CRF).

All medications will be coded using the World Health Organization-Drug Dictionary (WHO-DD).

- Concomitant medications are those taken at any time during the study treatment period, from the first study treatment use to the day of last study drug treatment, started before or during study treatment.

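### Relapse rate reduction is an uncontrolled change from a pre-study rate that overlaps entry selection, so it is biased upward by an amount the documents cannot fix

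*SAP*

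**What the plan says.** RRR is a secondary efficacy variable in Protocol 9.8.2 and SAP 2.1.3.2. SAP 2.4.3 gives the formula: "RRR will be calculated as the percentage reduction from baseline ARR to ARR at week 48".

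- **Baseline.** "Baseline ARR will be the sum of (Total # of Relapses Within 1 Year Prior to Screening collected from CRF"), divided by the number of subjects. No confirmation rule is given for this history count.
- **On study.** "ARR at week 48 is calculated as the ratio of the sum of all patients' confirmed relapse counts", divided by total treatment years. Counting starts at the first ublituximab dose and ends at Week 48 or early withdrawal. A relapse with an unknown start date is placed in this period unless there is enough information to exclude it.
- **Entry.** Criterion 3 in Protocol 3.1 admits subjects with two or more "relapses in prior 2 years or 1 relapse in the year prior to screening and/or" at least one Gd-enhancing lesion. Criterion 7 requires neurological stability for at least 30 "days prior to screening and baseline".
- **Relapse definition.** Protocol 7.1.4 requires a relapse to be "accompanied by objective neurological worsening consistent with an increase" in EDSS: at least 0.5 if baseline EDSS is above 1.0, and at least 1.0 if it is 0. The SAP does not say what makes a relapse confirmed.
- **Precision.** SAP 2.4.3 plans a 95% interval for the percentage relapse-free, but none for ARR or RRR.

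**The concern.** Two features of the formula push RRR up whatever the drug does. First, subjects are chosen partly because they relapsed recently, and the same year's count is then the comparator. Their later rate is expected to be lower even without treatment (regression to the mean). Second, a history count with no stated confirmation is compared with a confirmed count, so some events that would count in history may not count on study.

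What is at stake is interpretation. RRR is a listed efficacy result with no caveat and no interval. Protocol 1.3.1 cites rituximab reductions from baseline of 81% and 83%, which are figures of the same kind. An RRR from this trial could be set beside them and read as a drug effect.

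**Working it through.** The documents state no expected ARR or RRR, so there is no planned figure to reproduce. The check asks what RRR is expected when the drug has no effect.

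**Assumed inputs (none is in the documents).** Each candidate has a constant personal relapse rate, gamma distributed with mean m = 0.3 to 1.5 per year and shape k = 1 to 4. Counts are Poisson. A share g = 0 to 60% qualifies on a Gd lesion, independently of relapse history.

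**Derivation.** Without a Gd lesion, a candidate is excluded only with no relapse in the last year and at most one in the year before. At personal rate λ that has probability exp(−2λ)(1 + λ). Excluded candidates have no prior-year relapse, so if P is the share enrolled:

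- baseline ARR among those enrolled = m / P
- on-study ARR with no drug effect = [m − (1 − g)A] / P, where A = E[λ(1 + λ)exp(−2λ)]
- no-effect RRR = (1 − g)A / m

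With b = k/m, A = [b/(b + 2)]^k × [k/(b + 2) + k(k + 1)/(b + 2)²].

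**Central case, m = 0.5, k = 2.** b = 4, so A = (4/6)² × (2/6 + 6/36) = 0.4444 × 0.5 = 0.2222. RRR = 0.2222/0.5 = 44.4% with relapse-only entry, and 0.7 × 44.4% = 31.1% with g = 30%.

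**Range over k = 1 to 4:**

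| Mean rate per year | g = 0 | g = 30% | g = 60% |
|---|---|---|---|
| 0.3 | 54–66% | 38–46% | 21–26% |
| 0.5 | 38–49% | 26–34% | 15–20% |
| 1.0 | 19–24% | 13–17% | 7–10% |
| 1.5 | 11–13% | 8–9% | 4–5% |

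Simulation with 2,000,000 candidates per scenario agrees with these values.

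**Stability rule.** Requiring 30 relapse-free days before screening removes relapses from the baseline year and works the other way. In simulations that add it, RRR at 1.5 per year is 6–7% with relapse-only entry and −3% to 4% with 20–60% Gd entry. At 0.5 per year, shape 2, relapse-only, it is still 42.6%.

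**2-year baseline.** The 2-year rate among those enrolled is [m − (1 − g)B/2] / P, where B = E[λ exp(−2λ)]. In the central case B = 0.4444 × 0.3333 = 0.1481, so RRR = 1 − (0.5 − 0.2222)/(0.5 − 0.0741) = 34.8%, against 44.4%. The bias is smaller but remains, because criterion 3 also selects on two years.

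**Confirmation.** If a share c of relapses that would be reported in history is confirmed on study, RRR becomes 1 − c(1 − R), where R is the value above. With R = 31.1%, c = 0.9 gives 38.0% and c = 0.6 gives 58.7%. The documents do not give c.

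**No substitute control.** Two placebo subjects in each of six cohorts, for 28 days, give 12 × 28/365.25 = 0.92 person-years. These days precede the first ublituximab dose, so they are outside the on-study count.

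**Precision.** Six subjects for 48 weeks give 6 × 336/365.25 = 5.52 person-years. One relapse gives ARR 0.18 with an exact Poisson 95% interval of about 0.005 to 1.01. For 48 subjects (44.16 person-years), 11 relapses give ARR 0.25 with interval 0.12 to 0.45.

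**The case against.** The strongest reply is that the plan claims little for RRR. Protocol 9.8 says the study is not powered for treatment differences, and SAP 2.4 calls all tests descriptive. RRR is openly defined as a change from baseline, no test of it is specified, and the primary variable is B-cell response. ARR is listed separately, the percentage relapse-free has an interval, and SAP 2.1.1 already summarises "Number of relapses experienced within past 1 year and 2 years". All of this is correct, and it confines the harm to interpretation. It does not answer the point: those statements concern power and testing, not bias in a point estimate.

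A second reply concerns selection. Criterion 3 can be read to admit a subject on a Gd lesion alone, and two relapses in two years can be met with none in the last year. This stands. Not every subject is selected for a relapse in the baseline year, which is why the table falls as g rises.

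A third reply concerns the two counts. The case report form is not available, so unequal definitions are inferred from the lack of any stated rule for history. The re-consent text in Protocol 5.3 ties a confirmed relapse to Appendix C, which accepts a subjective report as an attack. If that is what the SAP means by confirmed, the mismatch is smaller than under Protocol 7.1.4. The default for unknown start dates also lowers RRR. These points stand: the mismatch probably raises RRR, but by an unknown amount.

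**Conclusion.** RRR as planned is uncontrolled, and its baseline overlaps entry selection. It also sets confirmed relapses against a history count with no stated confirmation. It is biased upward and should not be read as an estimate of drug effect. With both counts taken on the same definition, the expected RRR with no drug effect is about 4% to 66%, and about zero at the low end once 30-day stability is modelled. This rests on assumed rates of 0.3 to 1.5 per year, shape 1 to 4, 0 to 60% Gd entry, constant personal rates, and Gd status independent of relapse history. Unequal confirmation would add to it, and the start-date default would subtract.

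A reader might infer that a large reduction would appear with an inert drug, or that most of any observed RRR will be regression to the mean. The documents do not support either. They give no untreated rate, no between-subject variation and no Gd-only share, and the bias is small when rates are high or many subjects enter on Gd lesions. Nor does the gap in Protocol 1.3.1 between rituximab's 81% against its own baseline and 42.3% against placebo measure the bias, because the two figures come from different studies.

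The change should be made because it alters what can be concluded. No formal test in the plan depends on it.

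**What to change.** In SAP 2.4.3:

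1. Make ARR, by cohort and total, with an exact Poisson 95% interval, the main relapse result.
2. Label RRR *change from pre-study rate (uncontrolled)* and state that it does not estimate a drug effect.
3. Say which definition makes a relapse confirmed, and add a sensitivity RRR that counts all investigator-reported on-study relapses. This matches the history count ("Total # of Relapses Within 1 Year Prior to Screening collected from CRF") more closely. An exact match cannot be programmed, because the documents give no definition for history.
4. Show RRR against the 2-year pre-study rate, already a baseline variable, as a supplementary row, with a note that it reduces but does not remove the selection bias.

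The cost is SAP wording and a few extra table rows. Item 3 also needs a check that unconfirmed on-study relapses are recorded. RRR will look less favourable.
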